APPENDIX B. JOINT SAFETY REVIEW COMMITTEE (New appendix)		
See New wording column	
During the conduct of this study, a JSRC will review accumulating safety data in a blinded manner at 2 scheduled time points, as described below, to ensure the continuing safety of the study patients and to monitor study conduct issues.
 
The JSRC will be composed (at a minimum) of ≥ 1 of the study principal investigators, the study medical monitor or designee, the sponsor’s clinical lead, and the sponsor’s responsible pharmacovigilance physician. External consultants with relevant expertise may also be engaged as part of the JSRC, as applicable.
 
The JSRC will convene and review all available safety data after 20 patients (approximately 10 patients on IMP and 10 patients on placebo) have completed 8 weeks of treatment. A subsequent review will be convened after 50% of randomized patients (approximately 31 patients on IMP and 31 patients on placebo) have completed 8 weeks of treatment. A summary of the data will be reviewed in a blinded fashion. The JSRC will recommend whether to continue the study as designed, conduct protocol/ICF modifications, temporarily suspend enrollment and/or study intervention until some uncertainty is resolved, or discontinue the study.
 
The JSRC may also convene at any time during the study at the discretion of any of the JSRC members if new and pertinent safety issues arise.
 
The JSRC will document its recommendations with rationale and inform the study team as appropriate.
 
Additional details on the conduct of the JSRC sessions are outlined in the JSRC charter.
	Addition of JSRC
APPENDIX G. PRODUCT COMPLAINTS		
I. Clinical Product Complaints/Device Deficiency	I. Clinical Product Complaints/Device Deficiency	Text updated for consistency with the protocol template.

Original text with changes shown	New wording	Reason/Justification for change
For complaints involving a device/combination product or other retrievable item, it is required that the device/combination product (or item) be sent back to the sponsor for investigative testing whenever possible.	For complaints involving a device/combination product or other retrievable item, it is required that the device/combination product (or item) be sent back to the sponsor for investigative testing whenever possible.	Text updated for consistency with the protocol template.
Handling of Investigational Medicinal Product(s) and Devices at the Investigational Center(s)	Handling of Investigational Medicinal Product(s) and Devices at the Investigational Center(s)	Text updated for consistency with the protocol template.
If it is determined that the investigational center must return all IMP or devices , the sponsor will provide the information needed to handle the return.	If it is determined that the investigational center must return all IMP or devices, the sponsor will provide the information needed to handle the return.	Text updated for consistency with the protocol template.
A serious adverse event or the potential for a product quality problem existing beyond the scope of the complaint may be a reason to unblind the clinical supplies for an affected patient, if applicable .	A serious adverse event or the potential for a product quality problem existing beyond the scope of the complaint may be a reason to unblind the clinical supplies for an affected patient, if applicable.	Text updated for consistency with the protocol template.
The investigator will record in the source documentation a description of the product complaint, the initial determination whether the deficiency could have led to a serious adverse event (Section II) , and any actions taken to resolve the complaint and to preserve the safety of the patient.	The investigator will record in the source documentation a description of the product complaint, the initial determination whether the deficiency could have led to a serious adverse event (Section II), and any actions taken to resolve the complaint and to preserve the safety of the patient.	Text updated for consistency with the protocol template.

Original text with changes shown	New wording	Reason/Justification for change
See New wording column	
II. Assessment of Device Performance
 
Device performance will be assessed by device deficiencies and product complaints.
 
A device deficiency is defined as any inadequacy of an investigational medical device with respect to its identity, quality, durability, reliability, safety, or performance (Appendix Figure 1). This definition includes malfunctions, use errors, inadequate labeling (eg, unintelligible label, incorrect expiry date), and product complaints that are related to the device.
 
The investigator should make an initial determination whether the device deficiency could have led to a serious adverse event and notify the sponsor by completing the product complaint form provided by Teva and emailing it to [contact].
 
Device deficiencies with potential serious adverse device effect are defined as deficiencies that might have led to a serious adverse device effect if (Appendix Figure 1):
 
 • suitable action had not been taken (or) • intervention had not been made (or) • circumstances had been less fortunate 	Text updated for consistency with the protocol template.
See New wording column	New Appendix Figure 1 (Decision Tree for Device Deficiencies) was added	Text updated for consistency with the protocol template.

15.4. Administrative Letter 01 Dated 13 October 2020**ADMINISTRATIVE LETTER 01**

Study number: TV48574-AS-20031

Clinical Study Protocol

A 16-Week, Randomized, Double-Blind, Placebo-Controlled, Parallel-Group, Proof-of-Concept Study to Evaluate the Efficacy and Safety of TEV-48574 in Adults with T2-low/non-T2 Severe Uncontrolled Asthma, version dated 28 May 2020

IND number: 133677; EudraCT number: 2020-001927-15

13 October 2020

Dear Investigator:

The purpose of this letter is to clarify the procedures for the QuantiFERON[®] tuberculosis (TB) testing at screening. As per patient exclusion criteria (c), described in Section 4.2 of the protocol, a patient would be excluded if they tested positive for TB at screening by the QuantiFERON[®] TB Gold Test or had a history of latent or active TB. In order to protect against false positives, the steps outlined below should be followed when the QuantiFERON[®] TB Gold Test is drawn at screening and sent to the central laboratory:

- If the first QuantiFERON[®] TB Gold Test is negative, then the patient may proceed in the screening period.
- If the first QuantiFERON[®] TB Gold Test is positive, then a second sample should be drawn and sent to the central laboratory.
 - If the second QuantiFERON[®] TB Gold Test is positive (ie, results match the first test), then the patient will be a screen failure.
 - If the second QuantiFERON[®] TB Gold Test is negative (ie, results do not match the first test), then a third sample should be drawn and sent to the central laboratory.
 - If the third QuantiFERON[®] TB Gold Test is positive (ie, results match the first test), then the patient will be a screen failure.
 - If the third QuantiFERON[®] TB Gold Test is negative (ie, results match the second test), then the patient may proceed in the screening period.
 - Note that sites may choose to split the second and third samples and send one to the central laboratory and one to a local laboratory. However, the local laboratory result may not be used for decision making.

This change will be incorporated into the protocol during the next amendment, as applicable. Please ensure that this letter is maintained with the study protocol. Also, please provide a copy of this letter to your Institutional Review Board/Independent Ethics Committee for review and acknowledgement.

Please feel free to contact [REDACTED] if you have any questions or concerns regarding this letter.

Sincerely,

[REDACTED]

Clinical Development

APPENDIX B. JOINT DATA MONITORING COMMITTEE

During the conduct of this study, a JDMC will review accumulating safety data in a blinded manner at 2 scheduled time points, as described below, to ensure the continuing safety of the study patients and to monitor study conduct issues.

The JDMC will be composed (at a minimum) of ≥ 1 of the study principal investigators, the study medical monitor or designee, the sponsor's clinical lead, and the sponsor's responsible pharmacovigilance physician. External consultants with relevant expertise may also be engaged as part of the JDMC, as applicable.

The JDMC will convene and review all available safety data after 20 patients (approximately 10 patients on IMP and 10 patients on placebo) have completed 8 weeks of treatment. A subsequent review will be convened after 50% of randomized patients (approximately 31 patients on IMP and 31 patients on placebo) have completed 8 weeks of treatment. A summary of the data will be reviewed in a blinded fashion. The JDMC will recommend whether to continue the study as designed, conduct protocol/ICF modifications, temporarily suspend enrollment and/or study intervention until some uncertainty is resolved, or discontinue the study.

The JDMC may also convene at any time during the study at the discretion of any of the JDMC members if new and pertinent safety issues arise.

The JDMC will document its recommendations with rationale and inform the study team as appropriate.

Additional details on the conduct of the JDMC sessions are outlined in the JDMC charter.

APPENDIX C. CLASSIFICATION OF INHALED CORTICOSTEROIDS

Classification of ICS into low-, medium- and high-dose will be performed using the classification provided in GINA Global Strategy for Asthma Management and Prevention (2019 update), summarized in the following table.

Table 9: Classification of ICS into low/medium/high dose

Drug	Daily dose (µg)		
	Low	Medium	High
Beclomethasone dipropionate (CFC)*	200–500	>500–1000	>1000
Beclomethasone dipropionate (HFA)	100–200	>200–400	>400
Budesonide (DPI)	200–400	>400–800	>800
Ciclesonide (HFA)	80–160	>160–320	>320
Fluticasone furoate (DPI)	100	Not applicable	200
Fluticasone propionate (DPI)	100–250	>250–500	>500
Fluticasone propionate (HFA)	100–250	>250–500	>500
Mometasone furoate	110–220	>220–440	>440
Triamcinolone acetonide	400–1000	>1000–2000	>2000

CFC=chlorofluorocarbon propellant; DPI=dry powder inhaler; HFA=hydrofluoroalkane propellant

*Beclomethasone dipropionate CFC is included for comparison with older literature

APPENDIX D. QUALITY CONTROL AND QUALITY ASSURANCE

Protocol Amendments and Protocol Deviations

Protocol Amendments

No changes from the final approved (signed) protocol will be initiated without the prior written approval or favorable opinion of a written amendment by the IEC/IRB and national and local competent authorities, as applicable, except when necessary to address immediate safety concerns to the patients or when the change involves only nonsubstantial logistics or administration. The principal investigator at each investigational center, the coordinating investigator (if applicable), and the sponsor will sign the protocol amendment.

Important Protocol Deviations

Any deviation from the protocol that affects, to a significant degree, (a) the safety, physical, or mental integrity of the patients in the study and/or (b) the scientific value of the study will be considered an important protocol deviation. Important protocol deviations may include non-adherence on the part of the patient, the investigator, or the sponsor to protocol-specific inclusion and exclusion criteria, primary objective variable criteria, or GCP guidelines; noncompliance to IMP administration; use of prohibited medications. Important protocol deviations will be identified and recorded in the patient's source. All-important protocol deviations will be reported to the responsible IEC/IRB, as required.

When an important protocol deviation is reported, the sponsor will determine whether to withdraw the patient from the study or permit the patient to continue in the study, with documented approval from the medical expert. The decision will be based on ensuring the safety of the patient and preserving the integrity of the study.

Changes in the inclusion and exclusion criteria of the protocol are **not** prospectively granted by the sponsor. If investigational center personnel learn that a patient who did not meet protocol inclusion and exclusion criteria was entered in a study, they must immediately inform the sponsor of the important protocol deviation. If such patient has already completed the study or has withdrawn early, no action will be taken but the deviation will be recorded.

Information to Study Personnel

The investigator is responsible for giving information about the study to all personnel members involved in the study or in any element of patient management, both before starting the study and during the course of the study (eg, when new personnel become involved). The investigator must ensure that all study personnel are qualified by education, experience, and training to perform their specific task. These study personnel members must be listed on the investigational center authorization form, which includes a clear description of each personnel member's responsibilities. This list must be updated throughout the study, as necessary.

The study monitor is responsible for explaining the protocol to all study personnel, including the investigator, and for ensuring they comply with the protocol.

Study Monitoring

To ensure compliance with GCP guidelines, the study monitor or representative is responsible for ensuring that patients have signed the ICF and the study is conducted according to applicable SOPs, the protocol, and other written instructions and regulatory guidelines.

The study monitor is the primary association between the sponsor and the investigator. The main responsibilities of the study monitor(s) are to visit the investigator before, during, and after the study to ensure adherence to the protocol, that all data are correctly and completely recorded and reported, and that informed consent is obtained and recorded for all patients before they participate in the study and when changes to the ICF are warranted, in accordance with IEC/IRB approvals.

The study monitor(s) will contact the investigator and visit the investigational center according to the monitoring plan. The study monitor will be permitted to review and verify the various records (CRFs and other pertinent source data records, including specific electronic source document relating to the study) to verify adherence to the protocol and to ensure the completeness, consistency, and accuracy of the data being recorded.

As part of the supervision of study progress, other sponsor personnel may, on request, accompany the study monitor on visits to the investigational center. The investigator and assisting personnel must agree to cooperate with the study monitor to resolve any problems, errors, or possible misunderstandings concerning the findings detected during the course of these monitoring visits or provided in follow-up written communication.

Audit and Inspection

The sponsor may audit the investigational center to evaluate study conduct and compliance with protocols, SOPs, GCP guidelines, and applicable regulatory requirements. The sponsor's Global Clinical Quality Assurance, independent of Global Specialty Development, is responsible for determining the need for (and timing of) an investigational center audit.

The investigator must accept that competent authorities and sponsor representatives may conduct inspections and audits to verify compliance with GCP guidelines.

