4.4. Withdrawal Criteria and Procedures for the Patient

4.4.1. Withdrawal Criteria

In accordance with the Declaration of Helsinki (in accordance with the applicable country's acceptance) patients may completely withdraw from the study (ie, with no further study participation or contact) at any time for any reason. Patients may also voluntarily discontinue IMP and remain in the study for assessments. The investigator and/or sponsor may also discontinue a patient from IMP and/or withdraw a patient from the study, eg,

- in the event of intercurrent illness, adverse events, pregnancy, or any other reason concerning the health or well-being of the patient that indicates to the investigator that continued participation is not in the best interest of the patient, or

- if the patient is noncompliant with the study procedures and assessments or protocol-defined study restrictions or prohibited concomitant medication

Investigators are to discuss patients who may be considering discontinuing IMP or withdrawing completely from the study with the sponsor as soon as the site becomes aware of the situation.

Investigators should attempt to obtain information on patients in the case of withdrawal from the study or discontinuation from IMP. Results of any evaluations and observations, together with a narrative describing the reason(s) for withdrawal from the study or discontinuation from IMP, should be recorded in the source documents. The case report form (CRF) should document the primary reason for withdrawal from the study or discontinuation from IMP.

Discontinuation of IMP as described above and below does not include patients who discontinue IMP due to a LoAC event, as LoAC events are part of the planned conduct of the study.

If an adverse event is the primary reason for discontinuation of IMP or withdrawal from the study, this should be documented in the source and in the CRF including test results if applicable. Under these circumstances, monitoring should be continued until the event has resolved or stabilized, or until the patient is referred to the care of a health care professional, or until a determination of a cause unrelated to the study drug or study procedure is made.

The investigator should inform the sponsor as soon as possible of each patient who is being considered for withdrawal due to adverse events. Additional reports should be provided when requested.

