4.4.2. Discontinuation of IMP

Patients who discontinue treatment with IMP while remaining in the study are encouraged to complete early termination (ET visit) procedures as soon as possible after receiving their last dose of IMP and to complete the remaining study visits and assessments (with the exception of administration of IMP) including EOT and EOS within the original time frames based on date of randomization (DoR). The investigator should determine the reason for and the date of discontinuation of study treatment and record this information in both the source documentation and the CRF. The patient should not be considered withdrawn from the study due to interruption or discontinuation of IMP.

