5.10. Prior and Concomitant Medication or Therapy

Any prior or concomitant therapy, medication, or procedure a patient has had 4 weeks before screening through the end of the study will be recorded in the source documentation and in the CRF. Generic or trade name, indication, and dosage will be recorded. The sponsor will encode all therapy and medication according to the World Health Organization drug dictionary (WHO Drug). In addition, prior biologics and immunomodulatory therapies (biologics and non-biologics) should also be recorded in the source documents and in the CRF even if the end date was greater than 4 weeks prior to the initial screening visit.

The following medications will not be allowed during this study:

- Any systemic immunosuppressive or immunomodulatory agents (biological and non-biological) excluding systemic maintenance allergen immunotherapy and

systemic corticosteroids for the treatment of LoAC events including clinical asthma exacerbations).

Examples include but are not limited to:

- systemic corticosteroids (except for the treatment of LoAC/CAE during the study)
- methotrexate
- cyclosporine
- interferon
- omalizumab
- dupilumab
- mepolizumab
- benralizumab
- reslizumab
- anti-tumor necrosis factor monoclonal antibodies
- Non-protocol specified ICS+LABA
- Any investigational drug (biologic or non-biologic)
- Investigational drugs targeted against TL1A
- Live and attenuated vaccines

Note:

- Stable maintenance allergen immunotherapy will be allowed. Starting or build-up phase allergen immunotherapy will not be allowed.
- Completion of inactivated vaccination (including available inactivated COVID-19 vaccinations) is preferable at least 14 days before the first IMP dose, if possible. Inactivated vaccination during the study is recommended to be at least 3 days before and after IMP administration, if possible, or as required by local country regulations.

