9.1. Sample Size and Power Considerations

The primary efficacy analysis for this study will be the comparison between treatment groups of the proportion of patients experiencing a LoAC event during the 16-week treatment period. The study will be considered positive if the primary efficacy test indicates a statistically significant treatment effect versus placebo at the predefined significance level.

Sample size calculations were performed based on the following considerations:

In the Phase 2a study results for dupilumab, the observed LoAC rate in the placebo group was 44% (Wenzel et al 2013). The patients in that study had elevated peripheral blood eosinophil counts (≥ 300 cells/ μL). To estimate the LoAC rate that would have been observed in patients with peripheral blood eosinophil counts < 300 cells/ μL , the ratio of exacerbation rates observed between eosinophil count strata in the placebo groups of the dupilumab Phase 3 study were used (Castro et al 2018). This resulted in an estimated LoAC rate of 27% for the patients meeting the entrance criteria for the current study.

This study is designed to detect a 60% reduction in LoAC rate versus placebo; ie, a placebo group rate of 27% and a TEV-48574 group rate of 10.8%.

Based on the assumptions above, and assuming a 15% dropout rate during the study, 62 randomized patients per treatment group will provide 80% power to detect a treatment effect of 60% reduction in LoAC rate in the TEV-48574 group using a Chi-square test with one-sided alpha (Type I error rate) of 0.1.

An unblinded interim analysis is planned to re-assess the sample size and conduct a futility analysis as described in Section 9.13. If the sample size increases as a result of the interim analysis, the number of evaluable patients would be expected to increase proportionately.

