9.6.1.1. Primary Efficacy Analysis

The primary analysis will compare rates of LoAC between treatment groups using logistic regression with fixed effect for treatment, baseline FEV₁, weight, age group (<65 years vs ≥65 years), and gender as covariates. The primary analysis will be performed on the ITT analysis set. Patients who withdraw from the study or discontinue treatment due to lack of efficacy or due to an asthma-related adverse event will be analyzed as having experienced LoAC. Patients who withdraw from the study for other reasons will be analyzed as not experiencing LoAC. The treatment effect will be tested at a one-sided alpha of 0.1.

Subgroup analyses may be performed. These will be described and detailed in the SAP.

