### 6.2.2. Primary Efficacy Analysis

The primary analysis will compare rates of LoAC between treatment groups using logistic regression with fixed effect for treatment, age group (<65 years vs  $\geq 65$  years) and gender, as well as baseline FEV1 and baseline weight as covariates. Patients who withdraw from the study before the week 16 or early terminated the study treatment due to lack of efficacy, LoAC, or an asthma-related adverse event will be analyzed as having experienced LoAC. Patients who withdraw from the study before the week 16 without LoAC or early terminated from the study treatment without experiencing LoAC during the patient's treatment period (Section 1.7) for other reasons will be analyzed as not experiencing LoAC. Asthma-related adverse events will be determined by blinded data reviews prior to the final database lock.

The treatment effect will be tested at a one-sided alpha of 0.1.

The primary analysis will be performed on the ITT analysis set. The rates of LoAC for each treatment group, confidence intervals, and p-value will be displayed.

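### A patient withdrawn for prohibited controller use taken because asthma worsened can be scored as no LoAC, because every withdrawal or IMP stop for other reasons counts as a non-event

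*Protocol*

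**What the plan says.** **Scoring.** Protocol 9.6.1.1 counts withdrawal or treatment discontinuation for lack of efficacy or an asthma-related adverse event as LoAC. It then adds: "Patients who withdraw from the study for other reasons will be analyzed as not experiencing LoAC". SAP 6.2.2 extends the non-event rule to patients who stop study treatment without LoAC, who "for other reasons will be analyzed as not experiencing LoAC". SAP 1.7 states the same strategy and ends each patient's treatment period 14 days after the last dose.

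**Withdrawal.** Appendix D gives use of prohibited medications as an example of an important deviation. After such a deviation "the sponsor will determine whether to withdraw the patient from the study or permit the patient to continue in the study". The medical expert has to approve this, and the approval is put on record. Protocol 4.4.1 lets the investigator or sponsor stop IMP or withdraw a patient "if the patient is noncompliant with the study procedures and assessments or protocol-defined study restrictions or prohibited concomitant medication". Section 5.11 provides for withdrawal after noncompliance.

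**Prohibited controller.** The list in Protocol 5.10 includes "Non-protocol specified ICS+LABA". A note to 6.1.1 requires the controller regimen to stay stable except for the structured withdrawal or treatment of LoAC/CAE.

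**Review before lock.** In SAP 6.2.2 the blinded review decides which adverse events are asthma-related. It is not asked to classify reasons for withdrawal.

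**The concern.** Background controllers are taken away from patients with severe uncontrolled asthma, who know of the reductions. Worsening asthma is an obvious reason to go back to a controller without authorisation. If the site or sponsor then acts on the deviation, the recorded reason may be the prohibited medication and not the asthma. The rule turns that patient into a treatment success, and study withdrawal ends the collection of anything that could show otherwise.

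The primary endpoint is a single binary outcome with few expected events, so a few misscored patients matter. Equal loss in both arms costs power. Unequal loss biases the comparison in whichever direction the imbalance runs.

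**Working it through.** **1. Can a return to controller therapy miss LoAC?** The ICS component in Protocol 6.1.1 needs at least 4 times the most recent dose. From the twice-daily doses in Protocol Table 1:
- 250 back to 500: 500/250 = 2. Not met.
- 100 back to 250: 250/100 = 2.5. Not met.
- 100 back to 500: 500/100 = 5. Met.
- Restart from 0: the multiple is undefined, and neither document says how to treat it.

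So there are returns to a higher ICS dose that do not meet the ICS criterion, mainly while ICS is being stepped down.

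**2. The plan's own sample size.** Inputs from Protocol 9.1: rates 0.27 and 0.108, power 80%, 15% dropout, "using a Chi-square test with one-sided alpha (Type I error rate) of 0.1". With mean rate 0.189,

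n = [1.2816·√(2·0.189·0.811) + 0.8416·√(0.27·0.73 + 0.108·0.892)]² / (0.27 − 0.108)² = 51.8, so 52 evaluable per arm.

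52/0.85 = 61.2, so 62 randomized per arm. This reproduces the stated figure.

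**3. Reference power.** The ITT analysis scores every randomized patient, so 62 per arm is the right base. The 52 already excludes dropouts, and the patients at issue are themselves dropouts, so using 52 would remove them twice. Enumerating both binomials and rejecting when the pooled z exceeds 1.2816 gives exact power of 86.3% at 62 per arm when every true event is counted. Type I error with both rates at 0.27 is 10.1%.

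**4. Effect of lost events.** Let s be the share of true LoAC events scored as non-events by this route, so that an affected arm's observed rate is its true rate times (1 − s). The documents give no value for s. I assume 5% to 20% where both arms are affected, and 5% or 10% where only one is.

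| s | Both arms: power | Placebo only: power | Active only, no true effect: type I error |
|---|---|---|---|
| 0 | 86.3% | 86.3% | 10.1% |
| 5% | 84.6% | 82.1% | 13.4% |
| 10% | 82.7% | 77.1% | 17.5% |
| 20% | 78.6% | – | – |

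Expected placebo events are 62 × 0.27 = 16.7, so 5%, 10% and 20% are about 0.8, 1.7 and 3.3 placebo patients.

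**5. Sensitivity to one patient.** With 17 placebo events, 11 active events give z = 1.289 (significant, unadjusted) and 12 give z = 1.061 (not significant).

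**6. Do the other planned analyses repair it?**
- Per-protocol (SAP 3.4) excludes users of prohibited medication.
- Time to LoAC (SAP 6.3.1) censors them at withdrawal, which is informative if asthma was worsening.
- Multiple imputation (SAP 6.2.4) runs only when more than 5% of an arm leaves the study early for other reasons. Since 0.05 × 62 = 3.1, up to 3 such patients, with no other early leavers, would not trigger it. It imputes from observed LoAC by treatment and covariates, so it ignores what the withdrawal says about control. It does not cover patients who only stop IMP.

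None of these changes the primary result.

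**The case against.** **The path is narrow. This stands.** The patient must escape the daily FEV1/PEF and SABA criteria, the site alerts and the LoAC inquiry at each visit. The listed item is non-protocol ICS+LABA. LABA alone, LAMA and leukotriene antagonists are not named in 5.10, although restarting them departs from the 6.1.1 note. After about week 8 ICS is zero, and a restart from zero cannot be called clearly below 4 times.

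**The reason may be recorded correctly. This partly stands.** Protocol 4.4.1 and 4.4.3 ask for a narrative or explanation, and a site may enter lack of efficacy. Nothing requires it to do so when a deviation is also present.

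**Appendix D is not the root cause. This stands.** The cause is the other-reasons rule together with the window ending 14 days after the last dose. A patient kept in the study but off IMP is scored the same way, so longer follow-up alone would not change the primary result beyond that window.

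**Imputation will probably run. This stands.** Appendix J describes the anticipated 15% as early termination for reasons other than loss of control. That is 0.15 × 62 = 9.3 per arm, well above 3.1. The limits on what the imputation can recover remain.

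**Stronger readings that the documents do not support.** A reader might infer that Appendix D contradicts Protocol 4.4.2 and the ITT definition. It does not. Section 4.4.2 says "The patient should not be considered withdrawn from the study due to interruption or discontinuation of IMP", which concerns stopping IMP, and 4.4.1 separately permits withdrawal from the study. The ITT text includes data collected after discontinuation but does not promise that every patient is retained. A reader might also infer that the misscoring falls mainly on placebo and is therefore conservative. That is plausible if the drug works, but no arm split is given, and the active-only case inflates type I error.

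**Conclusion.** The concern holds in a limited form. A stated scoring rule, combined with stated powers to withdraw, can count a patient whose asthma worsened during the taper as a success, and no planned analysis corrects the primary result. It applies only where no LoAC criterion was met and recorded beforehand, and where the recorded reason is neither lack of efficacy nor an asthma-related adverse event.

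The size is uncertain. On the assumed shares, loss in both arms costs about 2 to 8 percentage points of power at 62 per arm. One-sided loss costs more power, or raises type I error, depending on the arm. These figures assume the design rates, an unadjusted chi-square test in place of the adjusted logistic model, and no other loss of events. They are illustrations and do not forecast how often this will happen. The change should be made because it is cheap and has to be fixed before unblinding.

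**What to change.** 1. **Protocol Appendix D, 4.4.1 and 5.11.** State that an important deviation alone does not end study follow-up. The patient stays for LoAC, CAE and safety assessments through week 16 and EOS unless consent is withdrawn or safety requires otherwise. IMP handling is left as it is.
2. **SAP 6.2.2 and 6.3.1.** Extend the blinded pre-lock review to classify the reason for each IMP stop or study withdrawal that involves prohibited asthma medication. Where the source narrative shows that worsening asthma drove it, treat the reason as lack of efficacy under the existing rule.
3. **SAP 6.2.4.** Add a sensitivity analysis, not conditional on the 5% trigger, that scores all such patients as LoAC and uses LoAC data collected after IMP stops through week 16.

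Scoring every controller restart as LoAC belongs in the sensitivity analysis and not in the primary one. There it would bypass the 4-fold ICS criterion and could turn simple non-adherence to the taper into failure.

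The cost is wording in both documents, one more item at a review already planned, one additional analysis, and follow-up to week 24 of a few patients who would otherwise have been removed.
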